12.0 DATA SAFETY AND MONITORING

- 12.1 Clinical information from the subjects will be recorded onto Case Report Forms and subsequently transferred into a computer database in a secure file at a reputable Clinical Research Organization that is experienced and operates in accordance with the applicable regulatory and HIPAA guidelines.
- 12.2 Accuray's clinical monitor will periodically analyze data and initial outcomes from SRS treatment in order to monitor for any information of clinical concern. Additionally, as warranted, safety information will be submitted by one of the lead site's investigators and/or Accuray's clinical monitor to Accuray's medical monitor.
- INDEPENDENT DATA SAFETY MONITORING BOARD: An independent Data Safety Monitoring Board (DSMB) will act as an advisory board to monitor patient safety and evaluate the efficacy of CyberKnife Stereotactic Radiosurgery for treating low and intermediate risk prostate cancer. The DSMB will conduct an independent objective review of the data to maximize the benefit to the trial participants. The DSMB will consist of 3 clinicians who are experts in or representatives of the fields of radiation oncology, stereotactic radiosurgery, urology, clinical trial methodology, and biostatistics. Membership will consist of persons completely independent of the investigators who have no financial, scientific or conflict of interest with the trial. Meetings of the DSMB will be held 4 times a year, with one annual meeting taking place face to face and the remaining meetings occurring via teleconference. The first board meeting will meet prior to initiation of the study to discuss the protocol and establish guidelines to monitor the study. The remaining quarterly meetings will be conducted via teleconference. The DSMB will monitor and evaluate all adverse events of all grades to establish relationship to the study procedures. Based on the review of toxicities summary the board will make recommendations to either continue, modify or terminate the study. After each meeting the board will provide the PI and Accuray with a written report concerning findings for the trial as a whole related to cumulative toxicities observed and any relevant recommendations related to continuing, changing, or terminating the trial. Information on cumulative toxicities and relevant recommendations will also be provided by Accuray to the rest of the participating sites to be shared with their IRBs.
- Adverse Events: An unanticipated adverse effect is defined by the FDA as any serious adverse effect on health or safety or any life-threatening problem or death caused by, or associated with, a device, if that effect, problem, or death was not previously identified in nature, severity, or degree of incidence in the protocol (including a supplementary plan), or any other unanticipated serious problem with a device that relates to the rights, safety, or welfare of subjects. Should any unanticipated adverse device effects occur during the course of the study, the clinical monitor will ensure that they are documented by the investigator and reported to the sponsor and the reviewing Institutional Review Board (IRB) as soon as possible, but no later than ten working days after the investigator first learns of the effect(s). The report regarding any unanticipated adverse device effect also will be provided to all other IRBs for the sites at which this clinical evaluation is being conducted. The clinical monitor, on behalf of the sponsor, will work with one of the lead site's investigators and Accuray's medical monitor to conduct an evaluation of such effects. Following this evaluation, if the determination is made that an unanticipated adverse effect presents an unreasonable risk to subjects, the clinical evaluation will be paused, if deemed appropriate

(to enable further investigation) or terminated as soon as possible. Termination shall occur no later than five working days after the sponsor makes the determination and no later than 15 working days after the sponsor receives notice of the unanticipated adverse device effect. In the event of termination, IRB approval will be obtained prior to resuming the clinical evaluation.

12.5 Below are criteria for early termination of either arm of the trial should an excessive number of patients experience a Serious Adverse Event (SAE). This depends upon the number so far enrolled and a criterion that identifies too high a rate. The stopping criteria differ after 48, 96 and 120 patients have been enrolled in both groups with additional applications when up to 144 and 178 have been enrolled in the low-risk group. Consistent with Section 11.2.1, we define an observed SAE rate of 20% as too high The statistical requirement is that for up to "m" patients enrolled, the number of observed SAEs must be few enough so that there is a 95% chance that the "true" rate does not exceed 20%.

	Serious Adverse Event (SAE) Stopping Criteria					
Participants to	Independently for both low- and interm-risk arms, stop an arm if					
be enrolled: 298	the number of grade 3-5 effects for that arm equals or exceeds:					
(178 low-risk,	Enrollment 1-48: 6 SAEs					
120 interm-risk)	Enrollment 1-96: 14 SAEs					
	Enrollment 1-120: 18 SAEs					
	Enrollment 1-144: 22 SAEs					
	Enrollment 1-178: 28 SAEs					

12.6 Regulatory Reporting: Any reports regarding safety issues and potential safety issues will also be provided to Accuray's Regulatory Affairs Department. Such reports will be evaluated and reported to the FDA and all applicable regulatory agencies, as deemed required.

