- 11.2.4 ACCRUAL RATE: the initial three months while institutions are obtaining IRB approval, therefore we do not expect to meet the targeted monthly accrual rate until after the first three months. The estimated accrual rate is 2.5 patients per study site per month. Expectations of 10 treating study sites assume an accrual period of approximately 11 months, or 14 month total
- 11.2.5 INTERIM ADJUSTEMENT IN ENROLLMENT: Interim analysis of the first 200 enrolled patients showed that 13 were actually ineligible because they were taking finasteride or dutasteride. Enrollment will thus be increased by 13 patients. Exclusion of patients on 5-alpha reductase inhibitors is clarified in section 5.12. We recognize that LHRH agonist/antagonist (e.g. leuprolide, goserelin, triptorelin, degarelix), hormone (e.g. DES), or peripheral blocker (e.g. flutamide, bicalutamide, nilutamide) administration given more than two months before enrollment may impact efficacy. Thus sample size (section 11.2) will be increased to insure enrollment is sufficient to achieve study objectives for the subgroup of patients naïve to such therapy. Interim analysis of the first 200 enrolled patients showed

 \Box

four had received LHRH agonists or peripheral hormone blockers. We could expect four more such patients to be enrolled through completion of the study. Thus enrollment should be increased by an additional eight patients, or 21 patients total. Applying the proportion of low to intermediate risk patients described in section 11.2.3, total enrollment will be increased to 129 intermediate-risk, and 190 low-risk (319 patient total). If subsequent interim evaluations show the estimated proportion of ineligible/lack-of-data cases is inaccurate, required enrollment will be accordingly adjusted.

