11.4 STATISTICAL METHODS

11.4.1 PRIMARY ENPOINTS

11.4.1.1 SAFETY: The upper limit of a one-sided 95% confidence interval for the expected proportion of patients experiencing a Serious Adverse Event (SAE) is estimated by U, where

$$U = \frac{(2np + Z_{0.05}^2) + Z_{0.05}\sqrt{Z_{0.05}^2 + 4pn(1 \cdot p)}}{2(n + Z_{0.05}^2)}$$

Here "p" is the observed proportion of patients experiencing an SAE . The CyberKnife intervention will be considered to be safe if this study's result verifies that U is not above $20\%^{80}$.

11.4.1.2 EFFICACY: The lower limit of a one-sided 95% confidence interval for the expected proportion of patients experiencing biochemical disease-free survival (bDFS) is estimated by L, where

$$L = \frac{(2np + Z_{0.05}^2) \cdot Z_{0.05} \sqrt{Z_{0.05}^2 + 4pn(1 \cdot p)}}{2(n + Z_{0.05}^2)}$$

Here "p" is the observed proportion of patients experiencing bDFS in either

ACCP001.4

arm of the trial. The CyberKnife intervention will be considered to be effective if this study's result verifies that L is not below 93%.

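### The SAE stopping table in 12.5 is still sized for 298 men, does not say how its rows are counted, and names no confidence limit

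*Combined protocol and SAP*

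**What the plan says.** Section 12.5 lets either risk arm be stopped for excess SAEs. It introduces the rule with "This depends upon the number so far enrolled and a criterion that identifies too high a rate". It says the criteria change after 48, 96 and 120 men in both groups, "with additional applications when up to 144 and 178 have been enrolled in the low-risk group". The stated requirement is that, for up to m men enrolled, "the number of observed SAEs must be few enough so that there is a 95% chance that the" true rate does not exceed 20%.

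The table applies to each arm separately. Its rows are all written from patient 1, for example "Enrollment 1-96: 14 SAEs", and the stop counts are 6, 14, 18, 22 and 28 at 48, 96, 120, 144 and 178. Its header still gives the number of participants to "be enrolled: 298", split 178 and 120.

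Two other sections bear on it. Section 11.2.5 says "total enrollment will be increased to 129 intermediate-risk, and 190 low-risk (319 patient total"). Section 11.4.1.1 judges safety against the same 20% using "The upper limit of a one-sided 95% confidence interval for the expected proportion of patients experiencing a Serious Adverse Event (SAE"), and the formula printed there is the Wilson score limit. Section 12.5 names no formula.

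**The concern.** This is the plan's only numeric SAE stopping rule, so it should cover everyone to be enrolled and lead two readers to the same action.

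The table ends before enrollment does. It can also be read in three ways. Suppose the sixth SAE among the first 48 men appears when 60 are enrolled:

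- Counted among the first 48 men, whenever the event occurs, the arm stops.
- As a running total, row 2 now applies and the arm continues with up to 13 SAEs.
- As a look made when 48 are enrolled, that look has already been passed with five, and the next comes at 96.

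Such a case is plausible. Section 11.2.4 says "The estimated accrual rate is 2.5 patients per study site per month" and expects 10 sites. Section 6.2 allows 90 days from registration to the first fraction, and section 11.2.1 includes late toxicity up to 5 years. Events in the first 48 men can easily appear after row 1 has been passed.

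**Working it through.** **Inputs.** Ceiling of 20% and 95% confidence, taken as one-sided, z = 1.645 (12.5); stop counts (12.5 table); Wilson formula (11.4.1.1); 190 and 129 men (11.2.5); 2.5 men per site per month at 10 sites (11.2.4); low to intermediate ratio 1.43:1 (11.2.3).

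**1. Reproducing the counts.** With x SAEs in m men and p = x/m:

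- Wald: U = p + 1.645 √(p(1−p)/m)
- Wilson: U = [2mp + z² + z√(z² + 4mp(1−p))] / [2(m + z²)]

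Example, m = 96. Wald at x = 13: 0.1354 + 1.645 × 0.0349 = 19.3%. Wald at x = 14: 0.1458 + 1.645 × 0.0360 = 20.5%. So the first count above 20% is 14, as printed. Wilson at x = 13: (26 + 2.71 + 1.645 × √47.66) / 197.4 = 20.3%, so Wilson stops at 13.

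| m | Printed stop count | Largest tolerated | Wald U of tolerated | Wilson U of tolerated | First count over 20%, Wald | First count over 20%, Wilson |
|---|---|---|---|---|---|---|
| 48 | 6 | 5 | 17.7% | 19.9% | 6 | 6 |
| 96 | 14 | 13 | 19.3% | 20.3% | 14 | 13 |
| 120 | 18 | 17 | 19.4% | 20.2% | 18 | 17 |
| 129 | none | – | – | – | 20 | 19 |
| 144 | 22 | 21 | 19.4% | 20.1% | 22 | 21 |
| 178 | 28 | 27 | 19.6% | 20.1% | 28 | 27 |
| 190 | none | – | – | – | 30 | 29 |

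Wald at the row end reproduces all five counts. Wilson gives one fewer in rows 2 to 5.

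**2. The same counts as running totals.** The smallest m at which the largest tolerated count has a Wald limit of at most 20% is 43, 93, 117, 140 and 175. The requirement therefore holds at 43–48, 93–96, 117–120, 140–144 and 175–178 men. Above 48 men it fails at 49–92 (44 numbers), 97–116 (20), 121–139 (19) and 145–174 (30). That is 113 of 130 enrollment numbers in the low-risk arm and 44 + 20 = 64 of 72 in the intermediate-risk arm. For instance, 13 SAEs are tolerated at 60, 72 and 84 men, where the Wald limit is 30.4%, 25.5% and 22.0% and the Wald stop count is 8, 10 and 12. By Wilson, no number above 48 meets the requirement.

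**3. How much lies ahead.** Section 11.2.5 reports on the first 200 men enrolled. If they split 1.43:1 (an assumption), that is 200 × 1.43/2.43 ≈ 118 low-risk and 82 intermediate-risk. Still ahead are 19 + 30 = 49 of the 113 low-risk numbers, and 83–92 and 97–116, or 30 of the 64, in the intermediate-risk arm.

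**4. Men with no count.** 190 − 178 = 12 low-risk and 129 − 120 = 9 intermediate-risk, whichever reading or limit is used.

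**5. Time spent in row 1.** 25 × 190/319 = 14.9 low-risk men a month, so 48 enroll in 3.2 months. 25 × 129/319 = 10.1 intermediate-risk men a month, so 48 enroll in 4.7 months.

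**6. False stops under the first-m reading.** Take SAEs as binomial at a true 10%, carry the count forward from row to row, and assume every event is counted while the arm is still open (an upper bound). The printed counts then stop the intermediate-risk arm with probability 36.3% and the low-risk arm with 36.5%. Most of this is row 1: P(6 or more of 48) = 34.7%. Adding Wald rows at 129 and 190 changes these by less than 0.1 point. Wilson counts give 38.4% and 38.6%.

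**The case against.** The best defence is that the counts themselves show what was meant. The rows are nested, all start at patient 1, and match a Wald limit at exactly 48, 96, 120, 144 and 178. Read as SAEs among the first m men, or as looks at m men, they meet the requirement at each m. This stands. A reader might infer from the running-total results that the table is miscalculated. The documents do not support that, because those failures exist only under one reading. The phrase about the number so far enrolled does lean towards that reading, so the wording needs settling.

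A reader might also infer that a definite number of men would be treated unnecessarily. That is not supported either. Any such number depends on when SAEs occur, which the plan does not give. The effect is small if most events are late, and at least 200 men are already enrolled.

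The Wilson mismatch is slight, and 11.4.1.1 governs the final analysis; it need not govern monitoring. That stands, but 12.5 should still say which limit it uses.

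On the uncovered men, carrying 28 and 18 forward would be stricter than either limit requires at 190 and 129. The DSMB and the sponsor's monitor also review events and can act, and the DSMB's first meeting is to set monitoring guidelines, which are not in these documents. So nobody goes unmonitored. Even so, the plan does not say the last counts carry forward, and the printed rule should not depend on guidelines a reader cannot see.

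**Conclusion.** The concern holds in a limited form. The firmest part is that the table does not match the current design: 12 low-risk and 9 intermediate-risk men have no stopping count under any reading. Next, the row definition is open, and the choice decides whether the table meets its own 95%/20% requirement: at every row end by Wald as first-m cohorts or row-end looks, but only in the last four to six men of each row as running totals. Least important is the unnamed limit, where Wald and Wilson differ by one SAE in rows 2 to 5 (tolerated counts have Wilson limits of 20.1–20.3%).

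The counts and limits follow directly from the documents, taking the 95% requirement as a one-sided upper limit. The share of the problem still ahead rests on the assumed split of the first 200 men. No number of men spared is claimed. This should be corrected, but it is a repair to the rule and does not show that the monitoring is unsafe.

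**What to change.** 1. Change the header to 319 men (190 low-risk, 129 intermediate-risk).
2. State that each row counts SAEs among the first m men enrolled in that arm, whenever they occur.
3. Name the limit and add the missing rows. With Wald, keep the printed counts and add 1–129: 20 and 1–190: 30, noting that this differs from 11.4.1.1. To match 11.4.1.1, use Wilson: lower rows 2 to 5 to 13, 17, 21 and 27, and add 19 and 29.
4. Only if running totals are intended, print counts by number enrolled for the enrollment still ahead. By Wald these include 99–104: 15; 105–110: 16; 111–116: 17; 123–128: 19; 129–133: 20; 180–185: 29; 186–190: 30.

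The cost is two rows and two or three sentences, or a longer table under item 4. Under the first-m reading, the Wald rows add almost nothing to the chance of stopping an arm at a true 10%, and Wilson adds about 2 points. The sponsor should know that this reading keeps row 1 active after 48 men are enrolled, and row 1 carries most of that chance. Per-number counts also raise it. Simulated from the first patient with all events assumed acute, the rise at a true 10% was 0–3 points with Wald over an 11-month accrual and 2–7 points over 22 months; it was under 0.5 point if half were late. Wilson per-number counts cost more (0–9 and 5–16 points, all acute).

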17.0 References

PROSPECTIVE EVALUATION OF CYBERKNIFE STEREOTACTIC RADIOSURGERY FOR LOW AND INTERMEDIATE RISK PROSTATE CANCER: HOMOGENOUS DOSE DISTRIBUTION

SCHEMA

^{*}Prescribed dose to PTV; prostate receives 8 Gy x 5

PATIENT POPULATION (see section 4.0 for complete eligibility)

Histologically-confirmed, adenocarcinoma of the prostate

Clinical Stage T1b - T2b, NX-0, MX-0

One of the following combinations:

- Gleason score 2-6 and PSA ≤ 20
- Gleason score 7 and PSA < 10

ECOG Performance Status 0-1

No prior prostate radiation or other definitive therapy

Required sample size: 319 patients.

ELIGIBILITY CHECKLIST

	Is there histologically proven prostate adenocarcinoma, biopsy within one year of enrollment?
(2-6)	What is the Gleason Score?
(T1b – T2b)	What is the clinical T-stage? (AJCC 6 th Edition)
(Y)	Is the patient clinical Nx or N0, and Mx or M0?
(0-20)	What is the patient's PSA?
	Does the patient fall into one of these risk groups (AJCC 6^{th} Edition): - Low: CS T1b-T2a, Gleason 2-6, PSA ≤ 10 - Intermediate: CS T2b, Gleason 2-6, PSA ≤ 10 , or CS T1b-T2b, and Gleason 2-6, PSA ≤ 20 ng/ml, or Gleason 7, PSA ≤ 10 ng/ml
(Y)	Is the prostate volume $\leq 100 \text{ cc}$?
(0-1)	What is the ECOG performance status?
(N)	Has the patient undergone prostatectomy or cryotherapy of the prostate?
(N)	Has the patient had radiotherapy to the prostate or lower pelvis?
	Has the patient implanted hardware near that would prohibit appropriate treatment planning or treatment delivery, in the investigator's opinion?
(N)	Has the patient had chemotherapy for a malignancy in the last 5 years?
` ,	Has the patient had an invasive malignancy (other than this prostate cancer, or basal or squamous skin cancers) in the last 5 years?
	Has the patient's androgen function been ablated during the past 2 months? See Section 5.12

ACCP001.4

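### The 12.5 stopping table is out of date (298 patients, not 319), mixes its counting unit, and its rows fall slightly short of the 95% assurance that 12.5 asks for

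*Combined protocol and SAP*

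**What the plan says.** **Enrolment.** The table in 12.5 is headed for participants to "be enrolled: 298" (178 low-risk, 120 intermediate-risk), and its last line reads "Enrollment 1-178: 28 SAEs". The schema states "Required sample size: 319 patients", and 11.2.5 says that "total enrollment will be increased to 129 intermediate-risk, and 190 low-risk (319 patient total").

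**Unit.** Section 12.5 opens with early termination "should an excessive number of patients experience a Serious Adverse Event (SAE"). In 11.4.1.1 the quantity p "is the observed proportion of patients experiencing an SAE". The requirement sentence of 12.5 instead limits the number of observed SAEs, and the table header refers to "the number of grade 3-5 effects for that arm equals or exceeds".

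**Limit.** Section 11.4.1.1 prints a one-sided 95% upper limit U (the Wilson score form) and calls the treatment safe if the "result verifies that U is not above" 20%. Section 12.5 cites 11.2.1, asks for 95% assurance that the true rate is no higher than 20%, and names no interval. The same paragraph also calls an *observed* rate of 20% too high, whereas 11.2.1 speaks of a *true* rate of 20%.

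**The concern.** This table is the plan's only numeric stopping rule for excess toxicity, so the DSMB should be able to apply it to every patient in one way. As written, no row covers the enrolment added by 11.2.5. A patient with two grade 3-5 effects counts once or twice, depending on the sentence used. A count that the table lets continue can exceed the limit by which the final safety result is judged. The missing rows cannot be filled in uniquely, because the method behind the printed ones is not stated.

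**Working it through.** **Inputs.** Rows 6, 14, 18, 22 and 28 at enrolments 48, 96, 120, 144 and 178 (12.5); 20% and one-sided 95%, z = 1.645 (11.4.1.1, 12.5); current cohorts 190 and 129 (11.2.5).

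**1. Enrolment gap.** 190 − 178 = 12 low-risk and 129 − 120 = 9 intermediate-risk patients. Together that is 21 of 319 (6.6%).

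**2. Reproducing the rows.** For each n, find the smallest count x whose upper limit exceeds 20%.

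- Wald: x/n + z√[(x/n)(1 − x/n)/n]. For 17/120: 0.1417 + 1.645 × 0.0318 = 19.4%.
- U of 11.4.1.1: [(2np + z²) + z√(z² + 4np(1 − p))] / [2(n + z²)]. For 17/120: (34 + 2.71 + 1.645 × 7.81) / 245.4 = 20.2%.

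| n | Printed row | Wald at row − 1 / at row | U at row − 1 | Exact P(X < row) at true 20% |
|---|---|---|---|---|
| 48 | 6 | 17.7% / 20.4% | 19.89% | 6.2% |
| 96 | 14 | 19.3% / 20.5% | 20.29% | 6.8% |
| 120 | 18 | 19.4% / 20.4% | 20.19% | 6.5% |
| 144 | 22 | 19.4% / 20.2% | 20.07% | 6.0% |
| 178 | 28 | 19.6% / 20.2% | 20.11% | 6.1% |

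Wald gives 6/14/18/22/28, all five printed rows. Unrounded U gives 6/13/17/21/27. U rounded to a whole percent also gives all five printed rows: every value in the U column rounds to 20%, and one count higher U is 22.40, 21.48, 21.13, 20.85 and 20.73%, all of which round above 20%.

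**3. Against 12.5's own requirement.** If the 95% assurance means at most a 5% chance of continuing at a true 20%, every printed row misses it. The assurance per look is 93.2% to 94.0%. Unrounded U would bring rows 96 to 178 to 3.8-4.0% but leaves row 48 at 6 (6.2%). A Clopper-Pearson limit gives 5/13/17/21/27.

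**4. The missing rows, for reference.**

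| n | Unrounded U | Wald | U to whole percent |
|---|---|---|---|
| 129 | 19 (18: 19.72%; 19: 20.58%) | 20 | 19 |
| 190 | 29 (28: 19.46%; 29: 20.04%) | 30 | 30 |

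With no row added, 19/129 or 29/190 continues with U above 20%. If the last printed row is carried forward, 18/129 or 28/190 stops an arm with U below 20%.

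**5. Effects or patients.** The documents give no number of effects per affected patient. Assuming 1.0 to 1.5, 18 effects at 120 means 18/1.0 = 18 down to 18/1.5 = 12 patients, or 15% down to 10% of the arm. A binomial limit applies to patients.

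**6. Practical size.** Applying the 1.43:1 ratio to the 200 patients reviewed in 11.2.5 gives 200 × 1.43/2.43 = 118 low-risk and 82 intermediate-risk, so row 96 has probably passed in the low-risk arm and row 48 in both. Suppose the stated rate is fully visible at each look, and replace the later printed rows by unrounded-U rows plus the new one. The chance of a later stop changes as follows:

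- low-risk past row 96: 0.7% to 1.9% at a visible 10%, and 61% to 76% at 20%;
- intermediate-risk past row 48: 2.5% to 5.7% at 10%, and 70% to 82% at 20%.

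At a visible 20% an arm passes row 48 only 6.2% of the time, so the gain there applies to a rare path.

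**The case against.** The strongest defence is that the table works as a monitoring aid. Each printed row gives one integer. Section 12.5 refers to 11.2.1 and not to 11.4.1.1, and an enrolment-based rule need not share the interval of the final 5-year analysis. Repeated looks also add protection: counting patients, the whole printed rule stops an intermediate-risk arm at a visible 20% with probability 1 − 0.0621 × (1 − 0.696) = 98%, and a low-risk arm with about 99%. That stands as a reason to call the effect small. It does not settle the per-look requirement that 12.5 itself states, and it assumes that 5-year toxicity is visible at the time of enrolment.

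Four stronger readings are tempting, and the documents do not support them.

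- *The table was built on a different interval.* Wald fits, but so does U rounded to a whole percent, and row 48 agrees with unrounded U. Only the one-count difference is established.
- *The text of 12.5 counts patients and only the header is wrong.* The requirement sentence and the rows count SAEs, so the text is itself mixed. The missing organ restriction is not peculiar to the table either: 11.4.1.1 also refers to SAEs in general, while 2.0 and 11.2.1 concern GI/GU toxicity. All-organ counting may be intended.
- *A few patients with several effects each would close an arm.* That needs an assumed ratio which the documents do not give.
- *The last 21 patients are unmonitored.* The DSMB meets four times a year, reviews adverse events of all grades, and can recommend termination. What is missing is a numeric boundary.

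**Conclusion.** The point holds and is minor. Two parts need no inference: the table was not carried from 298 to 319, and its counting unit is inconsistent across 12.5, its header and 11.4.1.1. The third part is arithmetic: rows 96 to 178 are one count above unrounded U, by at most 0.3 percentage points on the limit, and all five rows leave a 6.0% to 6.8% chance of continuing at a true 20%. That last comparison treats each look alone, counts patients, and reads the 95% requirement as a 5% chance of continuing. Where the printed rows came from remains open. The use of *observed* for the 20% rate is a wording error that does not alter the rows.

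**What to change.** Reconcile 12.5 with 11.2.1, 11.2.5 and 11.4.1.1:

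- Update the table header to 319 (190 low-risk, 129 intermediate-risk).
- Use one unit, patients, in the header, in both sentences of 12.5 and in 11.4.1.1. State whether all organs or only GI/GU toxicity is counted.
- Call the 20% a true rate.
- Name the limit and derive the rows still to come from it, including rows at 129 and 190. Alternatively, keep the printed rows and state the assurance they give, about 93-94% per look; rows at 129 and 190 are still needed.

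Which limit to use, and so which integers, is for the sponsor and the DSMB. The values in the working show only how far the answer depends on that choice.

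The cost is text edits, two added rows and, if unrounded U is chosen, up to four changed integers; no patients are added. Stricter rows slightly raise the chance of stopping an arm whose rate is acceptable, by about 1 to 3 percentage points at a visible 10%. Because data on the first 200 patients had already been reviewed, the change should carry dated DSMB agreement and be recorded as derived from the formula and not from the data.
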